attainment, 3) acceptability (Intrinsic Motivation Inventory – Interest/Enjoyment Subscale¹⁰), and Adverse & Serious Adverse Events (Timed Up-and-Go, Falls Efficacy Scale-International, Frequency of Events). Aim 2 outcomes, to assess effect size, will be average 10-day physical activity counts (ActiGraph monitors^{2, 11}) and self-report disability (Late-Life Function and Disability Index (LLFDI)^{12, 13}). In addition, Baseline descriptive measures include demographics, medications, cognition (Folstein Mini-Mental State Exam¹⁴), depression (Geriatric Depression Scale SF^{15, 16}), residual limb quality (Chakrabarty Scale¹⁷), sensory testing (Michigan Neuropathy Screen^{18, 19}), social support (Multidimensional Scale of Perceived Social Support), exercise readiness to change (Exercise Stages of Change^{20, 21}), prosthesis description, and comorbidities (Functional Comorbidity Assessment²²).

[figure not shown]

Fig. 1. Crossover study design.

Interventions and Duration

Thirty-two participants will be randomly assigned to two groups: GROUP1 or GROUP2. The home-based study design is intended to reduce participant burden by removing transportation and time barriers. There will be two participation periods of three months (Months 1-3 and 4-6). PABC intervention will occur Months 1-3 for GROUP1 and Months 4-6 for GROUP2. GROUP2 will participate in a no-exercise, attention control in Months 1-3. GROUP1 will have a no contact, intervention “wash-out” period in Months 4-6.

Evaluations will take place using the following schedule:

Baseline only: At Baseline testing, participants will also complete the following tests/measures/forms:

- 1) Folstein Mini-Mental State Examination
- 2) Geriatric Depression Scale SF
- 3) Chakrabarty scoring of residual-limb quality
- 4) Michigan Neuropathy Screen
- 5) Prosthetic description and Demographic Form
- 6) Functional Comorbidity Index
- 7) Multidimensional Scale of Perceived Social Support

Baseline, 3 and 6 months:

- 1) Timed Up-and-go
- 2) Two Minute Walk Test
- 3) Five Meter Walk
- 4) Single Limb Stance Test
- 5) Falls Efficacy Scale-International
- 6) Activity Measurement
- 7) Self-Efficacy for Exercise Scale
- 8) Intrinsic Motivation Inventory (IMI) – Interest/Enjoyment Subscale
- 9) LLFDI
- 10) Exercise Stages of Change
- 11) Prosthesis Evaluation Questionnaire – Mobility Section

Continuously: Falls, Adverse Events (AEs), and Serious Adverse Events (SAEs) will be recorded and reported as needed.

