Physical-Activity Behavior-Change (PABC) Intervention. The PABC intervention will occur during Months 1-3 for GROUP1 and Months 4-6 for GROUP2 (Fig.1). The intervention begins with a home visit in which the therapist delivers and outlines the PABC intervention and use of equipment (FitBit wearable sensor (FitBit Inc., Boston MA) and FitBit application on the tablet). The FitBit wearable sensor is designed specifically to provide user feedback through an

Table 2. PABC Intervention Overview	
Technique	General Content of Weekly Visit*
Education	1. Specific weekly educational message 2. Participant feedback on message 3. Therapist clarification as needed
Self Monitoring	1. Promote self-monitoring using FitBit 2. Self-monitoring goal creation
Tailored Feedback	1. Direct feedback from FitBit application
Barrier Identification	1. Participant input on barriers 2. Therapist assists identification 3. Falls & adverse events recorded
Promotion of Problem Solving	1. Ideas for addressing barriers 2. Participant and therapist provide input
Action Planning	1. Collaborative weekly action plan 2. Guideline: 3% ↑ in weekly steps 3. Goals based on individual needs
Encouragement	Therapist ends session by: 1. Reviewing the "take home" message 2. Reviewing action plan for next week 3. Acknowledging achievements

application on the home-based tablet. (FitBit Use Handout)

The first intervention week will be an accommodation period for the participant to interact with the equipment and establish baseline activity feedback. After the first week, an individualized participant action plan will be developed and the therapist will deliver the intervention following a semi-structured script (Tab.2). Weekly video-based interactions between participant and therapist (30 minutes) will occur during the 3-month intervention (12 visits) using the mobile-health tablets. The PABC intervention will require daily participant interaction with the tablet application. The tablet application is commercially available through FitBit and will provide feedback on number of steps taken and progress toward activity goals. Participants' activity will guide the goals for each week and barriers to reaching goals will be identified. The therapist will guide the participant in reasoning how to address any identified barriers to activity progression.

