Determining feasibility of the PABC intervention will set the stage for implementing a larger efficacy study. The expected result is that Veterans with LLA can be enrolled and retained in the PABC intervention with adherence to a 3% weekly increase in physical activity dose. In addition, the effect size is expected to be ≥ 0.80 . While similar interventions have been feasible and successful for other chronic disease populations, this trial will be the first to target chronic physical inactivity behavior for Veterans living with dysvascular LLA.

D.11. Participant Safety

Anticipated adverse events include falls and medical complications due to DM and PAD. A Safety Officer ([name]) for the study will meet with the PI quarterly to review study progress and adverse events. [name] is the Outpatient Medical Director for Rehabilitation Services at the Denver VAMC. [name] is also an Associate Professor in the Department of Physical Medicine and Rehabilitation at the University of Colorado. Beyond his clinical expertise, [name] has experience in outcomes research related to patients with LLA and functional exercise interventions. Fall risk will be monitored using the TUG test and Falls Efficacy Scale-International (FES-I) at all test points (baseline, 3M, 6M). Also, occurrence of falls will be recorded at each of weekly visit in both the intervention and control periods. Fall occurrences and other adverse events will be reported on a quarterly basis to the Safety Officer. The incidence of falls, defined as “inadvertently coming to rest on the ground, floor or other lower level, excluding intentional change in position”,⁸⁴ will be of particular focus. All study-related falls (possibly, probably, or definitely) will be tracked. If the total number of falls reaches 4, the Safety Officer will review incidence by group. If the number of falls for the intervention group exceeds that of the control group by 3 (10% of enrollment) at any time, the study will be suspended until an evaluation of study relatedness for each incidence is performed by the Safety Officer.

D.12 Potential Pitfalls and Alternative Strategies

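### D.11's continuous suspension rule for falls has no matching reporting step: scheduled reports to the Safety Officer are quarterly, nobody is assigned the by-group count, and a 3-0 split meets the margin before the required review at 4

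*Combined protocol and SAP*

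**What the plan says.** Section D.11 (Participant Safety) makes five statements that bear on this point.

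- Capture: "occurrence of falls will be recorded at each of weekly visit in both the intervention and control periods".
- Reporting: "Fall occurrences and other adverse events will be reported on a quarterly basis to the Safety Officer".
- Meetings: the Safety Officer "will meet with the PI quarterly to review study progress and adverse events".
- Review trigger: "If the total number of falls reaches 4, the Safety Officer will review incidence by group".
- Suspension trigger: "If the number of falls for the intervention group exceeds that of the control group by 3 (10% of enrollment) at any time", the study is suspended until the Safety Officer has evaluated the relatedness of each fall.

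The evaluation schedule in the synopsis adds: "Continuously: Falls, Adverse Events (AEs), and Serious Adverse Events (SAEs) will be recorded and reported as needed". On the length of a course, section D.5 says: "Weekly video-based interactions between participant and therapist (30 minutes) will occur during the 3-month intervention (12 visits".

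**The concern.** The suspension criterion is continuous, while the scheduled flow of falls to the person who must review and evaluate them is quarterly. The interval between reports is about as long as the intervention. The required by-group review also starts at a higher total than the smallest one at which the suspension margin can be met.

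Falls are a named anticipated adverse event in D.11, and the intervention deliberately raises walking in people whom section C.1 describes as at high risk of falling. This is the only pausing rule in the public document. If it is applied from the quarterly reports alone, it can act well after its own criterion was met, when some of those on PABC at the time have finished their course.

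**Working it through.** **Inputs.** From D.11: suspension margin 3, review trigger 4, reporting quarterly, capture weekly. From the synopsis: 32 participants. From D.5: a PABC course of 3 months and 12 visits.

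**The plan's own figure.** The margin is described as 10% of enrollment. 0.10 × 32 = 3.2, which rounds to 3 (3/32 = 9.4%). The figure reproduces.

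**Order of the two triggers.** Let *c* be the number of control falls when the intervention group first leads by 3. Falls add one at a time, so the first crossing occurs at exactly *c* + 3 intervention falls, at a total of (*c* + 3) + *c* = 2*c* + 3.

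- *c* = 0: split 3-0, total 3. Margin met; review at 4 not yet required.
- *c* = 1: split 4-1, total 5. Review already required.
- *c* = 2: split 5-2, total 7. Review already required.

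Only the 3-0 split is out of order. A 4-0 split can be reached only through 3-0.

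**Reporting lag.** One quarter is 52/4 = 13 weeks. If the Safety Officer learns of falls only from the quarterly report, the lag from crossing to recognition runs from near 0 to about 13 weeks. The upper end needs all the deciding falls to occur just after a report. If the count were checked at each weekly recording, the longest lag would be about 1 week.

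**Typical lag and reversals.** The documents give no fall rate, so these figures rest on assumption. Fall counts were taken as Poisson, with times spread evenly over a 13-week quarter and the tally starting at zero. There were 60,000 simulated quarters per setting. The last two columns refer to quarters with a crossing.

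| Mean falls per quarter (intervention, control) | Quarters with a crossing | Mean lag to quarter end | Lead back below 3 by quarter end |
|---|---|---|---|
| 2, 1 | 21% | 4.7 weeks | 14% |
| 3, 1 | 43% | 5.1 weeks | 11% |
| 3, 3 | 22% | 5.6 weeks | 33% |
| 4, 2 | 49% | 5.8 weeks | 16% |

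The longest simulated lag was 12.9 weeks. In the last column, a report giving only the quarter's totals would not show that the margin had been reached. A dated listing would show it, but late.

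**Who holds the count.** Weekly recording is done at the therapist's visits, and therapists know which period they are delivering. D.11 does not say who adds the falls up by group, how often, or who tells the Safety Officer that a trigger has been met. The synopsis wording names no trigger, recipient or deadline.

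**The case against.** The strongest reply is that D.11 describes a routine quarterly summary plus two event triggers, and that these can operate side by side. Treating the quarterly report as the sole channel would empty both triggers of meaning, and D.11 does not say it is the sole channel. The suspension clause does not depend on the review at 4. It gives the Safety Officer the evaluation after suspension and does not reserve detection to that person. Only testers are blinded (section D), section D.9 has the research team assess adverse event rates together with the Safety Officer, and the synopsis allows reporting outside the quarterly cycle. The review at 4 also serves splits that do not suspend, such as 2-2 and 3-1.

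Most of this stands. A reader might infer that the D.11 statements are incompatible, or that a breach would go unnoticed by everyone for a full PABC course. The documents support neither inference. A team that counted weekly could apply every sentence, and the therapists have the data to do so. Nor does a required review at 4 forbid an earlier look.

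The reply does not supply the missing step. For a 3-0 split, the suspension clause works only if someone is already counting by group, and D.11 asks for a by-group look only at 4. The as-needed wording is too general to fill the gap, and it sits uneasily beside the specific quarterly statement.

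**Conclusion.** The point holds as a mismatch between a continuous rule and its stated reporting. On the D.11 wording, recognition by the Safety Officer could lag by up to about 13 weeks in the worst case, and by about 5 to 6 weeks on average under the assumed rates. A lead that has reversed by quarter end could be missed in a quarterly total. The ordering problem is confined to the 3-0 split.

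I attach no probability to a 3-0 start. The documents give no fall rate, and D.11 does not say how GROUP2's falls in Months 4-6 are classed. If they count as intervention falls and all 32 participants complete, there are 16 + 16 = 32 participant-quarters on PABC against 16 on control, so a calculation from equal exposure would mislead.

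Two limits apply. Section D.7 refers to a Human Subjects section that is not in the public document, and a faster route might be described there. The one-week figure applies only where weekly visits take place; GROUP1 has no contact in Months 4-6.

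**What to change.** Ask the sponsor and the Safety Officer to reconcile four statements: the quarterly reporting in D.11, the as-needed reporting in the synopsis, the by-group review at a total of 4, and the continuous margin of 3. The reconciled text should name who keeps the by-group count (someone other than the blinded tester), how often it is updated, and how a met trigger reaches the Safety Officer. The frequency should be enough for the rule to operate as stated, using the falls already captured weekly. The thresholds, the order of the triggers and the suspension rule itself are for them to set.

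The cost is protocol wording, a simple tally and a few more reports to the Safety Officer. No new visits or measurements are needed.

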We will recruit older Veterans with dysvascular LLA (1-5 years after LLA) to participate in the PABC intervention, which uses established VA Health Care system technology and evidence-based intervention methods. The five key dimensions of feasibility to be assessed are whether Veterans: 1) can successfully participate in the intervention (practicality), 2) tolerate physical activity progression (implementation feasibility), 3) are interested and enjoy the intervention (acceptability), 4) complete the intervention safely (safety), and 5) respond to the intervention with increased activity and decreased disability (responsiveness).^{31,32} Measures of physical activity and disability will be used to establish effect size estimates for the PABC intervention, with the intention of planning a future clinical efficacy trial. Testing will occur at baseline (pre-intervention), three months (end of intervention), and six months, using a two-group randomized crossover design.

Primary Aim: Determine feasibility of using the PABC intervention with older Veterans who have dysvascular LLA by assessing: 1) practicality (measured by retention rate), 2) implementation feasibility (measured by dose goal attainment), 3) participant acceptability (measured by the Intrinsic Motivation Inventory (IMI) – Interest / Enjoyment Subscale), and 4) safety (measured with Adverse and Serious Adverse Events).

Hypothesis 1.1: Retention rate will be at least 85% over the PABC intervention period (i.e., ≤15% attrition).

Hypothesis 1.2: At least 75% of participants will meet the dose goal of a 3% average increase in daily steps per week, across the three months of intervention.

Hypothesis 1.3: Participants will indicate PABC intervention acceptability with a mean score of ≥ 5/7 on the IMI – Interest / Enjoyment Subscale.

Hypothesis 1.4: There will be similar rates of study related (definitely, probably, possibly) adverse events between groups during the first three months (period of direct comparison of intervention versus control).

Secondary Aim: Establish effect size estimates of the PABC intervention (responsiveness)

using physical activity and self-report disability outcomes.

Hypothesis 2.1: The PABC group will have increased activity counts and less self-reported disability than the control group at Month 3, each with effect size estimates ≥ 0.80 (Cohen's d).

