The proposed pilot study is a randomized, tester-blinded design assessing PABC intervention feasibility (Aim 1) and effect size (Aim 2). Randomization ($n=32$) will create two groups (GROUP1 or GROUP2) using computer-generated random blocks of 2 and 4, stratified by amputation level (transtibial and transfemoral). An investigator not involved with testing or intervention ([name]) will conceal group allocation. A crossover design is used to simultaneously accomplish the aims and optimize recruitment (Fig.2). The PABC Intervention will be delivered to both groups (GROUP1 during Months 1-3 and GROUP2 during Months 4-6). The crossover design provides $n=32$ for assessing Aims 1 and 2. Intervention effect retention will be tested at six months for GROUP1 ($n=16$).

D.1. Setting

The study will occur at the VA Geriatric Research Education and Clinical Center (GRECC), where Drs. [name] and [name] have dedicated positions ([name] (GRECC Director)). Intervention delivery will occur with the participant at home and therapist at a VA site with access to tablet interface software (e.g. VA Jewell Motion Analysis Lab or VA Clinical Building South, using VA-supplied and approved mobile-health tablets and wearable activity sensors (FitBit)).

D.2. Participants

Thirty-two participants will be recruited from the Denver VAMC. The target sample is older Veterans diagnosed with PAD and/or DM, who have major LLA. We expect $<15\%$ attrition, with a goal of 26 participants completing.

D.3. Eligibility Criteria

Inclusion criteria: ≥ 50 years of age, LLA 1-5 years prior, Type II DM and/or PAD, and

ambulatory without human assistance, in the home or better using a prosthesis, with assistive device as needed, with assistive device as needed. Exclusion criteria: wheelchair as primary form of locomotion, trauma or cancer-related etiology of the LLA, unstable heart condition, uncontrolled hypertension, acute systemic infection, cancer, recent stroke (within 2 years), or lower extremity wound or ulcer that limits ambulation.

D.4. Recruitment Strategies

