All participants will be recruited from the Denver VA Medical Center (VAMC) or Veterans that are receiving care outside of the VA system in our core-group of regional hospitals. [name] and [name] will use the Amputation Clinic database and meet with the rehabilitation teams to obtain names of Veterans meeting the inclusion criteria. A research team member will then contact the potential participant in person or by letter and ask for permission to explain and complete a brief screening form to determine the Veteran's eligibility. We will increase the recruitment pool for this study from our previous studies, by allowing participants with both transfemoral and transtibial amputation. Recruitment from the Denver VAMC is expected to be feasible based on Denver VAMC data (47 new Veterans seen in rehabilitation for new major LLA in last 18 months).

D.5. Intervention

The home-based study design is intended to reduce participant burden by removing transportation and time barriers. There will be two participation periods of three months (Months 1-3 and 4-6). PABC intervention will occur Months 1-3 for GROUP1 and Months 4-6 for GROUP2 (Fig.1). GROUP2 will participate in a no-exercise, attention control in Months 1-3. GROUP1 will have a no contact, intervention "wash-out" period in Months 4-6.

Study Initiation. A physical therapist will initially meet with the participant at the participant's home to: 1) obtain informed consent and authorization, 2) deliver and orient the participant to wearing an activity monitor (ActiGraph Inc. Pensacola FL), and 3) assess the prosthetic fit and function (Prosthetic Evaluation Questionnaire). If prosthetic fit and function concerns are identified, the participant will be given recommendations for seeing his/her prosthetist, which must be met before beginning the intervention. The participant will wear the ActiGraph monitor for 10 days after the initial visit. The ActiGraph monitor will be used only for outcome data (not intervention) and provides no feedback to participants.

Following the initial visit, participants will be randomized (GROUP1 and GROUP2).

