- H1.1) Retention rate will be assessed using a cut off of 15% attrition (i.e., loss of >6 participants). Mean attrition rate will be compared to the null value of 15% using a one-sample t-test ($\alpha=0.05$). This attrition rate is considered feasible based on previous activity change programs for patients with DM or PAD.^{5, 83}
- H1.2) Dose goal attainment will be assessed by the proportion of participants achieving the goal of 3% average weekly increase in steps, based on activity gains in other intervention studies.^{3, 12, 78} The ability to attain a 3% average weekly step increase for <75% of the participants will be considered a negative result. The proportion of participants attaining a 3% average weekly step increase will be reported (95% CI) and compared to the null value of 75% using a one-sample binomial proportions test ($\alpha=0.05$).
- H1.3) Acceptability of the intervention will be measured with the IMI Interest and Enjoyment subscale, with a mean score of <5/7 considered a negative acceptability result.¹⁰ Mean IMI Interest and Enjoyment score will be compared to the null value of 5.0 using a one-sample t-test ($\alpha=0.05$).
- H1.4) Adverse and serious adverse event (AE/SAE) rates (events/participant) will be compared between groups for Months1-3 (PABC intervention for GROUP1, attention control for GROUP2). We expect similar AE/SAE rates between groups (assessed by Safety Officer and research team).

Aim 2 (Effect Size and Preliminary Efficacy of PABC Intervention): Effect size of the PABC intervention will be calculated with Cohen's d using mean and standard deviation for change in activity counts and LLFDI scores. Statistical inference of group differences for calculation of sample size estimates will be based on linear models with activity counts and LLFDI scores as outcome variables. Explanatory variables in each model will include primary medical diagnosis (PAD, DM, or both), group, and baseline activity count or LLFDI score.

D.10. Expected Outcomes and Interpretation

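### Does the falls suspension trigger in D.11 need a written rule for attributing falls once both groups have had the intervention?

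*Combined protocol and SAP*

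**What the plan says.** D.11 (Participant Safety) sets two numerical triggers for falls. The first is a review: "If the total number of falls reaches 4, the Safety Officer will review incidence by group". The second is a suspension: "If the number of falls for the intervention group exceeds that of the control group by 3 (10% of enrollment) at any time", with the study paused until the Safety Officer has evaluated the study relatedness of each fall. Just before these, D.11 states that "All study-related falls (possibly, probably, or definitely) will be tracked" and that "occurrence of falls will be recorded at each of weekly visit in both the intervention and control periods". Falls and other adverse events also go to the Safety Officer every quarter.

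The design section (D) states that "The PABC Intervention will be delivered to both groups (GROUP1 during Months 1-3 and GROUP2 during Months 4-6"). Under D.5, GROUP2 has the attention control in Months 1-3 only, and "GROUP1 will have a no contact, intervention" wash-out in Months 4-6.

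The protocol uses the intervention-control contrast for safety in two other places. Hypothesis 1.4 compares study-related adverse event rates "between groups during the first three months (period of direct comparison of intervention versus control"). D.9, under H1.4, says adverse event rates "will be compared between groups for Months1-3 (PABC intervention for GROUP1, attention control for GROUP2").

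**The concern.** In a parallel-group trial the suspension sentence would need no gloss. Here the label attached to a participant changes at Month 3. GROUP2 leaves control and starts PABC, GROUP1 leaves PABC and enters a period without contact, and nobody is in a control period any longer. D.11 uses raw counts, names no window, gives no denominator and does not refer to H1.4. Enrolment runs over six quarters (Section E), so at many calendar dates some GROUP2 participants are in control while others are on PABC. The attribution question would therefore arise while the rule is in use.

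Three readings can be put to the words: Months 1-3 only; PABC time against control time for everyone; or GROUP1 against GROUP2 throughout. The second compares unequal exposure. The third counts GROUP2's falls on PABC as control falls, and also depends on whether GROUP1's wash-out falls are captured. D.11 is also not explicit on whether all falls or only study-related falls count. This is the plan's only numerical suspension trigger. If the readings were equally open, the same data could pause the trial under one and not under another.

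**Working it through.** **The plan's own figure.** 10% of 32 enrolled is 0.10 × 32 = 3.2, rounded to 3 (3/32 = 9.4%). The threshold reproduces.

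**Planned exposure** (16 per group, three-month periods, no dropout):
- PABC: 32 × 3 = 96 participant-months, of which 16 × 3 = 48 fall in Months 1-3.
- Attention control: 16 × 3 = 48.
- GROUP1 wash-out: 16 × 3 = 48.

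**Drift at equal fall rates.** Write r for counted falls per participant-month. The expected excess on the intervention side is:
- Months 1-3 only: 48r − 48r = 0.
- By treatment received: 96r − 48r = 48r, which is 0.48, 0.96, 2.4 and 4.8 falls at r = 0.01, 0.02, 0.05 and 0.10. It reaches 3 on average at r = 3/48 = 0.0625.

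The documents give no fall rate, so these values of r are assumptions. They imply 144r = 1.4, 2.9, 7.2 and 14.4 falls over PABC and control time together.

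**Chance of ever reaching +3 with no true difference.** For a balanced comparison each fall is equally likely on either side, so by reflection P(ever ≥ 3) = P(D ≥ 3) + P(D ≥ 4), where D is the final difference (Skellam). For 48 against 48:
- r = 0.01: 0.0085 + 0.0010 = 0.9%
- r = 0.02: 0.0347 + 0.0076 = 4.2%
- r = 0.05: 0.1214 + 0.0532 = 17.5%
- r = 0.10: 0.2064 + 0.1265 = 33.3%

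The other readings were simulated: 40,000 trials per scenario, enrolment of 4, 4, 6, 6, 6, 6 per quarter as in Section E, random blocks of 2 and 4, Poisson falls, no dropout, the difference checked after each fall, and wash-out rate equal to control rate.

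| Reading | r = 0.01 | 0.02 | 0.05 | 0.10 |
|---|---|---|---|---|
| Months 1-3 only | 1.0% | 4.3% | 17.9% | 33.4% |
| By treatment received | 5.4% | 19.0% | 54.0% | 79.0% |
| GROUP1 v GROUP2, wash-out falls not counted | 0.7% | 2.9% | 9.4% | 15.7% |
| GROUP1 v GROUP2, wash-out falls counted | 4.2% | 13.5% | 33.4% | 49.4% |

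The first row agrees with the closed form. These figures take an excess of exactly 3 as enough. If more than 3 is needed, treatment received gives about 1%, 8%, 38% and 68%, and Months 1-3 about 0.1%, 1%, 8% and 20%. The levels fall and the spread remains.

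**Which reading the text supports.** H1.4 describes the first three months as the direct comparison of intervention with control. D.9 repeats that window and names GROUP1 as PABC and GROUP2 as attention control. H2.1 compares the PABC group with the control group at Month 3. No section calls GROUP2 control while it is on PABC, which leaves the third reading without support. The mention of intervention and control periods in D.11 concerns when falls are recorded, not how they are compared. Because entry is staggered, a check at any time is compatible with a comparison confined to each participant's first three months. As to which falls count, the sentence on tracking study-related falls stands directly before both triggers and is their natural antecedent.

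**The case for a change.** The best case for a change is that D.11 does not borrow H1.4's window or its events-per-participant denominator, so a careful reader could still apply the rule by treatment received. The chance of a pause would then rise from about 18% to 54% at r = 0.05. The review at four falls is also by group and inherits the same ambiguity. Under the Months 1-3 reading, half of planned PABC time (48 of 96 participant-months) lies outside the suspension trigger. With PABC truly doubling the rate (0.10 against 0.05), the chance of a trigger is about 57% on Months 1-3 and about 93% by treatment received. Falls in GROUP1's wash-out are to be recorded continuously according to the Synopsis, while D.11 describes only weekly visits in the other periods.

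What stands is that D.11 has no attribution sentence, that it does not say who first classifies relatedness, and that it does not describe how wash-out falls are captured. The rest carries less weight. A between-group count has no parallel control in Months 4-6, so leaving that time out follows from the design. GROUP2's PABC time is still covered by weekly recording, quarterly reports and the total-falls review. Wash-out falls do not enter a Months 1-3 comparison, and GROUP1 has an in-home visit at six months where they can be reported. If only study-related falls count and they are rare (r = 0.01), every reading lies between about 1% and 5%.

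**Conclusion.** No change to the plan follows. D.11 leaves out a detail that the rest of the protocol largely supplies: the intervention-control contrast belongs to Months 1-3, where exposure is 48 against 48 participant-months and raw counts are a fair comparison. The large figures, up to 79% at equal rates, need both the less supported treatment-received reading and an assumed rate of 0.10 counted falls per participant-month. They also assume no dropout and independent Poisson falls.

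A wrong reading would cost a temporary pause or a later review, with the Safety Officer evaluating each fall either way. No aim, endpoint, estimate or sample size depends on it. Writing out the window, which falls count and how wash-out falls are captured would add clarity but would not correct a wrong result. The sponsor and the Safety Officer can confirm these points, reconciling D.11 with H1.4, D.5 and the Synopsis, when they set up the falls log. The threshold and the action remain theirs, and nothing here bears on whether they are right.
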